**PrEP Readiness Interventions for Supporting Motivation
(PRISM)**

**[name], ABAP (Contact MPI) & [name],
MPH (MPI)**

NCT04205487

August 7, 2024

UM-IRB

20180823: Stimulant-Using MSM and PrEP

(PRISM project)
[name], Principal Investigator

NCT04205487

Version Number #10.1

Version Date: 04/2023

IRB Study Number: 20180823
Version #10.1; April 2023

1) Protocol Title

Adaptive Intervention Strategies to Optimize PrEP Clinical Evaluation and Uptake in Stimulant-Using Men

2) Objectives*

The overarching goal of this formative research is to examine whether—and in what combination—contingency management (CM) and motivational interviewing (MI) can facilitate entry of stimulant-using men who have sex with men (MSM) into the pre-exposure prophylaxis (PrEP) care continuum.

- Aim 1.** Augment CM and MI with content to facilitate entry into the PrEP care continuum by conducting qualitative interviews with PrEP healthcare team members and stimulant-using MSM.
- Aim 2.** Examine the *feasibility and acceptability* of adaptive treatment strategies combining CM with MI to promote clinical evaluation for PrEP, PrEP uptake, and PrEP care retention.
- Aim 3.** Document implementation factors relevant the *scalability* of CM and MI such as perceptions of community-based HIV prevention providers to inform a full-scale sequential multiple assignment randomized trial (SMART) of the interventions.

3) Background*

Preliminary Data: There are no relevant preliminary data for this R34 project where the primary objective is to obtain preliminary data for a planned R01 proposal.

Significance: The CDC estimates one-in-six MSM will acquire HIV in their lifetime, including one-in-two Black MSM and one-in-four Hispanic/Latino MSM. PrEP is highly effective for preventing HIV infection, but many MSM who are at elevated risk for HIV are experiencing difficulties with initiating and remaining on PrEP. As a biomedical intervention, PrEP offers tremendous protection against HIV infection without necessitating changes in sexual behavior. PrEP can also serve as a gateway into regular HIV testing as well as comprehensive sexual and mental health care. There is an urgent need to augment as well as tailor evidence-based CM and MI interventions to facilitate entry of stimulant-using MSM into the PrEP continuum.

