Inclusion Criteria for Phase II: Participants will be included in the pilot SMART based on:

- 18 years of age or older
- Sexually active MSM
- Reports using methamphetamine, powder cocaine, or crack-cocaine at least one day in the past 3 months
- HIV-negative (confirmed at baseline)
- Meets CDC criteria for PrEP eligibility
- Not currently prescribed PrEP

Exclusion Criteria for Phase II: Participants will be excluded if they: a) are under 18 years of age; b) are not a man who has sex with men; or c) are unable to provide informed consent at the assessment visit in English.

5) Procedures Involved*

Phase I – We will conduct formative qualitative data collection to support our efforts to modify the extant CM and MI protocols to include content relevant to the PrEP care continuum. Key informant interviews and focus groups with 10-12 PrEP healthcare team members (e.g., physicians, nurse practitioners, social workers, and benefits navigators) will facilitate our efforts to obtain a more nuanced understanding of barriers and facilitators to optimizing the PrEP care continuum in stimulant-using MSM. We will also ask PrEP healthcare team members to elaborate regarding how they manage the complex care needs of stimulant-using MSM (e.g., addressing problematic patterns of stimulant use, safer injection practices, and referrals to substance use disorder and mental health treatment). The qualitative

IRB Study Number: 20180823

Version #10.1; April 2023

interview guide for our work with providers is attached. Because PrEP healthcare team members are completing this one time study visit in their professional role, we are requesting a waiver of signed informed consent.

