In-depth qualitative interviews with stimulant-using MSM. In-depth interviews with stimulant-using MSM will be approximately one hour and cover topics such as history of stimulant use, attitudes and beliefs about PrEP. Those who are not on PrEP will be asked to describe on barriers and facilitators to accessing PrEP. Those who are currently taking PrEP will be asked to describe how they successfully

IRB Study Number: 20180823

Version #10.1; April 2023

navigated the process of initiation and strategies they are implementing to achieve prevention effective PrEP adherence. After completing the interview, participants will complete a brief survey to assess demographic information and efforts to navigate the PrEP healthcare continuum (see attached). Stimulant-using MSM will receive \$40 for completing this one time study visit.

[figure not shown]
Phase II – We will conduct a pilot SMART with 70 HIV-negative, stimulant-using MSM who meet CDC criteria for PrEP eligibility.

First Stage Intervention. After completing a baseline assessment and a brief run-in period, participants will be randomized to complete a 3-month CM intervention or a two-session MI intervention that were developed as part of our Phase I activities.

Second Stage Intervention. Three months after this first-stage randomization, participants will complete a second informed consent prior to a 3-month follow-up assessment to determine whether they are responders.

[figure not shown]
Experimental Conditions. Responders will be classified as those who have started PrEP, the primary outcome. Responders will continue with assessments only.

Participants who have not responded to the initial intervention will be randomized again to either: 1) continue with assessments only; or 2) switch to the other intervention (i.e., CM+MI versus MI+CM). An overview of the pilot SMART procedures is provided in the figure below. Below we describe each of the procedures relevant to executing this pilot SMART.

Telephone screen. Stimulant-using MSM will complete a brief telephone screen to determine eligibility for enrolling in the pilot SMART based on inclusion criteria above for Phase II (see attached). This telephone screen has been modified to include items relevant to the novel coronavirus (COVID-19), which are also attached. The figure below describes the participant flow for the pilot SMART.

PRISM 2.0 Study Flow Diagram

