Data Safety and Monitoring Plan. The University of California, Los Angeles Data Safety and Monitoring Board in Addiction Medicine (DSMB-AM) has agreed to serve as the DSMB of record for this trial. The DSMB will hold annual meetings to monitor trial progress the DSMB chair will be notified within 72 hours of any adverse event (AE) or serious adverse event (SAE) regardless of whether it is judged to be related to study procedures by the study team. All self-report data will be collected using a secure server behind the University of Miami firewall. Any paperwork or data containing identifiers will either be in a secured cabinet in a locked office or on a password protected server. Staff receive extensive training in data management and security protocols.

9) Risks to Subjects*

- Privacy risks including a breach of confidential information
- Psychological risks including negative reactions to study measures
- Legal risks related to forced disclosure of information related to substance use
- Social and economic risks related to discrimination if there was a breach of confidential information such as substance use
- Possible injury from rectal DBS or rectal swab collection

10) Potential Benefits to Subjects*

All participants in this study will receive some form of evidence-based treatment to reduce stimulant use (i.e., MI or CM). However, we are uncertain if these interventions will yield meaningful benefits for engagement along the PrEP care continuum. The proposed research has the potential to advance our understanding of promising intervention approaches to simultaneously target stimulant use and difficulties with engagement along the PrEP care continuum in MSM. This will be one of the first trials to test potentially scalable strategies for optimizing medical

IRB Study Number: 20180823

Version #10.1; April 2023

evaluation for PrEP and PrEP uptake in a high priority population of stimulant-using MSM.

11) **Vulnerable Populations***

Although stimulant-using MSM are marginalized and underserved, this population is not classified as vulnerable under 45 CFR Part 46. At this time, we do not plan to conduct any study procedures with incarcerated participants.

12) **Setting**

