PRISM primary and secondary outcomes. Adaptive interventions that are embedded in a SMART can be compared via the Weighted and Replicated (W&R) method (Nahum-Shani et al., 2012). However, given the feasibility and acceptability nature of this study we instead descriptively compared three groups by aggregating across the first-stage and second-stage randomizations (see Figure 1): MI-only (arms D and E), CM-only (arms A and B), and MI+CM (arms C and F). Specifically, our efforts to examine the primary and secondary outcomes proceeded in four steps. First, demographic characteristics and meth use severity were stratified by first-stage randomization status (i.e., MI versus CM) to ensure randomization was successful (see Table 1). Second, intervention assignment was collapsed into the three groups described above. Third, because pilot trials do not provide reliable effect size estimates (Kraemer & Kupfer, 2006), we did not conduct statistical tests or comment on the magnitude of CM, MI, or MI+CM effects. Instead, we provide descriptive statistics for primary and secondary outcomes at six months stratified by intervention assignment. Fourth, we examined correlates of verified PrEP use (versus no PrEP use) over the 6-month follow-up, irrespective of first- or second-stage randomization status.

Figure 1. Pilot SMART procedures

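### The only randomised comparison with a no-further-intervention side, switch versus assessments only in month-3 non-responders, is named in no analysis, and the SAP's three groups are split by response instead

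*Protocol*

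**What the plan says.** Protocol section 2 (Objectives) gives the overarching goal as to "examine whether—and in what combination—contingency management (CM) and motivational interviewing (MI) can facilitate entry of stimulant-using men" into the PrEP care continuum. Aim 2, just below, is narrower: the feasibility and acceptability "of adaptive treatment strategies combining CM with MI to promote clinical evaluation for PrEP, PrEP uptake, and PrEP care retention".

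Protocol section 5, First Stage Intervention: "participants will be randomized to complete a 3-month CM intervention or a two-session MI intervention". Section 10 confirms that nobody goes without: "All participants in this study will receive some form of evidence-based treatment to reduce stimulant use (i.e., MI or CM".

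Protocol section 5, Experimental Conditions: "Responders will be classified as those who have started PrEP, the primary outcome". Responders go on to assessments only. Non-responders are "randomized again to either: 1) continue with assessments only; or 2) switch to the other intervention (i.e., CM+MI versus MI+CM".

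The planned analyses are these:

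- Protocol section 8, Feasibility and Acceptability: t-tests comparing the two switch sequences with each other.
- Protocol section 8, Quantitative Analyses: logistic regression for differences by arm, with arm not defined.
- SAP, primary and secondary outcomes: the Weighted and Replicated method is mentioned and set aside. Six-month outcomes are described, without tests, in three groups: "MI-only (arms D and E), CM-only (arms A and B), and MI+CM (arms C and F". A last step looks at correlates of verified PrEP use regardless of either randomisation.

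**The concern.** The stated goal has two parts: whether the interventions help, and in what combination. With CM against MI and no third arm, the first stage cannot address the first part. The second stage is the only place where chance decides between a further intervention and none, so it is the only source of an unbiased view of what adding the other intervention does. None of the listed analyses reports it.

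The SAP's grouping does not stand in for it. Membership of MI+CM depends on not having started PrEP by month 3, and starting PrEP is itself an outcome. A reader who wants to know about combination will look along the row from MI-only and CM-only to MI+CM, and will see a difference that the grouping rule produces by itself. The planned display could make a useful switch look harmful.

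**Working it through.** **Inputs.** The pilot SMART has 70 men (protocol section 5, Phase II). The documents give no response rate, uptake rate or second-stage allocation ratio, and the protocol says that no formal power analysis was done, so there is no planned precision figure to reproduce. The one sum that can be checked agrees: about 30 Phase I men + 70 Phase II men = 100, as in section 16.

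**Assumptions.** First stage 35 and 35; second stage 1:1; no attrition; the same month-3 response rate *r* in both first-stage arms, 10-50%; uptake between months 3 and 6 among non-responders *q*, 5-30%; month-3 responders counted as uptake at six months. Figure 1 is not shown. I take arms C and F as the switch arms, which follows from the group labels and the design.

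**Where the men go.**

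- Single-intervention groups: 70*r* responders plus 35(1 - *r*) assessments-only non-responders.
- MI+CM: 35(1 - *r*) switchers, all of them non-responders.

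**Expected uptake if switching has no effect.**

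- Single-intervention: (70*r* + 35(1 - *r*)*q*) / (70*r* + 35(1 - *r*)). With equal *r* and *q*, MI-only and CM-only each show this same value.
- MI+CM: *q*.
- Gap against MI+CM: 2*r*(1 - *q*) / (1 + *r*).

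At *r* = 30% and *q* = 15%: (21 + 24.5 × 0.15) / (21 + 24.5) = 24.675 / 45.5 = 54%, against 15%. The gap is 39 points.

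Gap in percentage points, MI+CM looking worse:

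| Month-3 response | *q* = 5% | *q* = 15% | *q* = 30% |
|---|---|---|---|
| 10% | 17 | 15 | 13 |
| 30% | 44 | 39 | 32 |
| 50% | 63 | 57 | 47 |

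**If switching truly adds 20 points.** At *r* = 30% and *q* = 15%, MI+CM shows 35% against 54%, so a real benefit appears as 19 points of harm. At *r* = 10% it appears as a benefit of only 3 to 7 points (20 - 17.3 and 20 - 12.7).

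**What the omitted contrast could show.** Here I allow for loss: 80-90% retained to month 3 and 50-80% of those not responding (assumed). Non-responders: 70 × 0.8 × 0.5 = 28 to 70 × 0.9 × 0.8 = 50. That is 14 to 25 per side pooled, and about 7 to 12 per side within one first-stage arm. Newcombe 95% intervals for 30% versus 15%, treating the proportions as exact:

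| Per side | Interval for the difference (points) |
|---|---|
| 25 (pooled, best case) | -8 to +37 |
| 14 (pooled, low case) | -16 to +43 |
| 12 (one first-stage arm) | -18 to +45 |
| 7 (one first-stage arm) | -28 to +52 |

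These calculations are for PrEP starts. Protocol section 8 names PrEP medical evaluation as the primary outcome, whereas section 5 gives that name to PrEP start; the two passages need reconciling. I have not sized the gap for evaluation, because non-responders may already have been evaluated before month 3.

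**The case against.** The strongest reply is that this is a formative pilot and says so. The aims are feasibility, acceptability and scalability. Protocol section 8 says that pilots should not be about effect size, section 10 admits uncertainty about benefit, and the SAP states that it neither tests nor comments on the size of CM, MI or MI+CM effects. This stands, and it limits the seriousness of the point. It does not make the three-group table a fair display, because the columns will be read side by side whether or not a test is attached.

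The undefined arm in the protocol's logistic regression may have been meant to include the second-stage arms. That is possible, but the contrast is not named, and the SAP has pooled groups instead. The arm letters are inferred, as noted above. The SAP is written in the past tense, so a change now affects reporting and not conduct.

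A reader might go further in four ways that the documents do not support:

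- *PrEP use starts at zero by eligibility* ("Not currently prescribed PrEP")*, so any rise will be credited to the interventions.* No before-after analysis of PrEP is planned; the outcomes are counted over follow-up or described at six months by group.
- *Stimulant use can only fall from its entry value.* That is true only of a yes/no measure over the eligibility window. The criterion is a minimum of one day, so the amount of use can move either way.
- *The results will be taken into the planned R01 as evidence of efficacy.* The protocol says that the project gathers preliminary data for an R01, but nothing says that uptake will be presented in that way, and the SAP disclaims it.
- *The second-stage contrast would settle whether CM or MI works.* Both sides have already been assigned one of them. It shows only whether adding the other helps men who have not started PrEP.

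**Conclusion.** The point holds as one of reporting, and it is not a defect in the trial's conduct. The randomised switch versus assessments-only comparison is absent from every named analysis, and the SAP's substitute is confounded by month-3 response. Under the stated assumptions and no effect of switching, MI+CM would look 13 to 63 points worse than the single-intervention groups. The direction follows from the design alone, provided that C and F are the switch arms and response is similar in the two first-stage arms. The size depends on the assumed *r* and *q*, for which the documents give no figures.

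No redesign, larger sample or hypothesis test is called for. The part of the goal that asks whether CM or MI beats no intervention stays unanswered by this design whatever is tabulated.

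**What to change.** In SAP step three, and in the protocol's Quantitative Analyses paragraph:

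1. Add one descriptive table of PrEP evaluations and PrEP starts occurring after second-stage randomisation, switch versus assessments only among month-3 non-responders, by first-stage arm and pooled. Give counts, 95% intervals for each proportion and for the difference, and no test. Show how many men on each side had already been evaluated by month 3.
2. State that MI+CM set beside MI-only and CM-only is not a randomised comparison, because group membership depends on month-3 response.
3. State that the new contrast shows only whether adding the other intervention helps non-responders, not whether CM or MI is better than no intervention.

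The table uses data already collected and needs no new participants or visits. The price is wide intervals, particularly within one first-stage arm, and a more modest statement about combination. Rewording the overarching goal would gain little, since the aims beneath it already limit the work.

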Stage 1 informed consent. Prior to the baseline assessment, participants will review an online consent with a study staff member of zoom detailing the procedures for the first three months of the pilot SMART and indicate whether they consent to participate.

We have elected implement sequential informed consents for this project for two primary reasons. First, the study procedures are complex and dependent on whether participants respond to the first-stage intervention. Sequential informed consent procedures enhance the comprehension of this complex SMART protocol. Second, because one of the interventions involves receiving CM incentives this could create a scenario where participants initially randomized to MI choose not to respond in order to have another chance to receive CM incentives in the second-stage intervention. Conducting sequential informed consenting substantially mitigates this concern because participants are not aware of the second-stage interventions until the 3-month follow-up assessment. Given these ethical and logistical concerns, we believe sequential informed consenting is a reasonable solution.

Baseline assessment. Due to the challenges presented by COVID-19, we are requesting a waiver of written consent to review the Stage 1 consent with

IRB Study Number: 20180823

Version #10.1; April 2023

participants over zoom at baseline. We will follow-up with remote HIV testing. Participants will be asked to indicate whether they consent to participate in the study and continue with the baseline assessment via Zoom. The baseline quantitative and qualitative assessment includes a detailed battery of measures and a brief in-depth qualitative interview. A codebook of the baseline quantitative measures as well as the qualitative interview guide are attached. Participants will receive a \$50 Amazon gift card or cash application payment for completing this assessment.

Remote HIV testing. To ensure that participants meet the inclusion criteria for Phase II, they will be asked to complete remote HIV testing by mailing in a saliva sample from a kit that our team will send to their home. Participants will receive \$25 as an Amazon gift card or cash application payment for completing remote HIV testing. Those who test positive for HIV will be excluded from this trial and referred for confirmatory testing in their local community.

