Non-reactive (HIV-) test results will be delivered to participants as part of their randomization visit. For those who do not respond to attempts to schedule their randomization visit, after 2 months their non-reactive HIV test results will be emailed to the email address on file via a secure, encrypted University of Miami email. This report does not contain any PHI.

All study staff also receive ongoing training and supervision from [name] (a licensed psychologist) on delivering HIV test results and providing counseling to individuals experiencing acute distress. All staff will receive training in procedures for immediate linkage to confirmatory HIV testing. Participants residing in Miami-Dade county who are test positive for HIV will be referred for confirmatory testing and anti-retroviral therapy (ART) with [name].

Randomization visit. Approximately one week after baseline, participants who are confirmed to be HIV-negative will attend a separate randomization visit. Those randomized to CM will be introduced to incentives for PrEP clinical evaluation and uptake. Participants randomized to MI will receive their first session of this intervention. All participants will receive a \$20 Amazon gift card or secure cash application payment for attending the randomization visit.

CM intervention protocol. Participant randomized to CM will complete a 3-month CM protocol where they will be eligible for CM incentives for documentation that they have been evaluated for PrEP by a medical provider (\$50) and filled a prescription for PrEP (\$50) in the three months following randomization. Total possible CM incentives are \$100 per participant, which will be provided in Amazon gift cards or secure cash application payment.

MI protocol. Participants in the MI intervention will complete two individually delivered sessions via zoom designed to enhance intrinsic motivation and self-efficacy for taking the first steps towards starting PrEP and addressing the

IRB Study Number: 20180823

Version #10.1; April 2023

intersection of substance use and HIV risk. Session 1 focuses on supporting efforts of participants to be medically evaluated for PrEP. Session 2 focuses on addressing the intersection of substance use and HIV risk. A detailed protocol for this 2-session MI intervention is attached. Participants will receive a \$20 Amazon gift card or secure cash application payment for completing each MI session via zoom.

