Stage 2 informed consent. Prior to completing the 3-month follow-up assessment, participants will provide informed consent for the Stage 2 of the pilot SMART. This consent will clarify that participants may be invited to participate in a CM or MI intervention based on the responses to the survey questions and prior intervention assignment. Due to the challenges presented by COVID-19, we are requesting a waiver of written consent to review the consent with participants over zoom.

3-month follow-up assessment with second-stage randomization. After completing the informed consent process, we will re-administer quantitative measures from the baseline assessment via Zoom, and those who have not started PrEP will be classified as non-responders. All non-responders will complete the second-stage randomization to either: 1) continue with assessments only; or 2) switch to the other intervention (CM+MI versus MI+CM). Those randomized to receive CM or MI will receive these intervention consistent with the protocols described above. Responders will continue with assessments only. Participants will receive a \$50 Amazon gift card or secure cash application payment for completing this assessment. Participants will have a 30-day window (+1 month) to complete their follow-up assessments.

6-month follow-up assessment. We will re-administer the quantitative measures from the baseline assessment and a qualitative exit interview (see attached) via zoom. Participants will receive a \$50 Amazon gift card or secure cash application payment for completing this assessment. Participants will have a 30-day window (+1 month) to complete their follow-up assessments.

6) Risks

These study procedures meet the criteria for minimal risk research activities. However, possible risks include: 1) a breach of confidentiality; and 2) negative psychological reactions to study procedures.

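### The Stage 2 consent ties a CM or MI invitation to survey answers just before the month-3 answer that sets responder status, so the protocol's safeguard against gaming does not reach that answer

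*Protocol*

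**What the plan says.** Protocol section 5, Stage 1 informed consent, names the risk. MI-first participants might "choose not to respond in order to have another chance to receive CM incentives in the second-stage intervention". Sequential consent is said to reduce this substantially "because participants are not aware of the second-stage interventions until the 3-month follow-up assessment".

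The order of events at month 3 is given in several places in section 5:

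- Second Stage Intervention: "participants will complete a second informed consent prior to a 3-month follow-up assessment to determine whether they are responders".
- Stage 2 informed consent: "Prior to completing the 3-month follow-up assessment, participants will provide informed consent for the Stage 2 of the pilot SMART". That consent will say that "participants may be invited to participate in a CM or MI intervention based on the responses to the survey questions and prior intervention assignment".
- 3-month follow-up assessment, on when the survey is given: "After completing the informed consent process, we will re-administer quantitative measures from the baseline assessment via Zoom".
- The same paragraph, on how status is then set: "those who have not started PrEP will be classified as non-responders".

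Section 20 repeats that the second consent precedes the month-3 assessment. Non-responders are then randomized to assessments only or to the other intervention. Responders have assessments only.

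Under the CM intervention protocol, payment is for documents showing a PrEP evaluation ($50) and a filled prescription ($50) "in the three months following randomization". Second-stage CM follows the same rules. Each of the two MI sessions pays $20.

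The SAP (PRISM primary and secondary outcomes) pools participants into MI-only, CM-only and MI+CM, describes outcomes at six months, runs no tests and does not comment on effect size.

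**The concern.** The safeguard works by withholding information. It protects the decision whether to start PrEP during the first three months, because participants do not yet know what non-response leads to. It has lapsed when the month-3 question is asked: minutes earlier, the participant has been told that his answers and prior arm bear on an invitation to CM or MI. An MI-first participant who has already started PrEP could then deny it.

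Responder status decides who enters the second randomization, so a false denial has two effects. It puts a responder into a randomization meant for non-responders. If he is switched, it also moves him from MI-only to MI+CM in the six-month table, where he looks like an MI+CM success. The pilot is meant to inform a full-scale SMART, so the same visit order could carry over to a trial in which the comparison is tested.

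**Working it through.** **1. Order.** Section 5 gives: Stage 2 consent, then survey, then classification, then second randomization. The safeguard ends at the first step and the answer is given at the second.

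**2. What a concealer could gain.** The protocol's CM maximum reproduces: 50 + 50 = $100. The second-stage ratio is not stated; 1:1 is assumed.

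- MI-first, new evaluation and new fill both qualify: 0.5 × 100 = $50 expected ($33 to $67 if the chance of a switch is 1/3 to 2/3).
- MI-first, only a new fill qualifies: 0.5 × 50 = $25 ($17 to $33).
- MI-first, nothing new qualifies: $0.
- CM-first: 0.5 × 2 × 20 = $20 expected, with a ceiling of $40. If concealing means giving up an unclaimed $50 fill payment from Stage 1, the net is 20 − 50 = −$30. If that payment was already claimed, the study holds a document that contradicts the denial.

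Any positive incentive therefore lies mainly with MI-first participants, and it may be nil.

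**3. Head count (illustration).** Only the total of 70 comes from the protocol. Assumed: 35 per first-stage arm; response *r* = 20-40% in both arms; a share *c* = 10-20% of MI-first starters conceals; late uptake *u* = 10-20% among true non-responders; responders are counted in the single-intervention groups (the SAP figure is not shown).

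Concealers *k* = 35*rc*, from 35 × 0.2 × 0.1 = 0.7 to 35 × 0.4 × 0.2 = 2.8. Half are switched: 0.35 to 1.4 people.

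**4. Shift in six-month PrEP uptake.**

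- MI+CM without concealment: *N* = 35(1−*r*), *X* = *uN*. With it: (*X* + *k*/2)/(*N* + *k*/2).
- MI-only without concealment: *n* = 35*r* + 17.5(1−*r*), *x* = 35*r* + 17.5*u*(1−*r*). With it: (*x* − *k*/2)/(*n* − *k*/2) if unswitched concealers count as PrEP users at month 6, or (*x* − *k*)/(*n* − *k*/2) if they keep denying.

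| Case | MI+CM | MI-only, counted | MI-only, still denying |
|---|---|---|---|
| *r* 0.2, *c* 0.1, *u* 0.2 | 5.6/28 = 20.0% → 5.95/28.35 = 21.0% (+1.0) | 9.8/21 = 46.7% → 9.45/20.65 = 45.8% (−0.9) | → 9.1/20.65 = 44.1% (−2.6) |
| *r* 0.4, *c* 0.2, *u* 0.1 | 2.1/21 = 10.0% → 3.5/22.4 = 15.6% (+5.6) | 15.05/24.5 = 61.4% → 13.65/23.1 = 59.1% (−2.3) | → 12.25/23.1 = 53.0% (−8.4) |

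These cases are the extremes over the assumed ranges, except that the counted MI-only fall peaks at −2.4 near *r* = 0.345.

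**5. Against sampling error.** In the second case the MI+CM standard error is √(0.1 × 0.9/21) = 6.5 points, so +5.6 is 0.86 of it. For MI-only it is √(0.614 × 0.386/24.5) = 9.8 points, so −8.4 is also about 0.86 of it. Every shift is below one standard error.

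**6. Lower concealment.** The documents give no basis for 10-20%. At 2-5%, the same two combinations of *r* and *u* give MI+CM +0.2 to +1.5 points, and MI-only −0.2 to −0.6 (counted) or −0.5 to −2.0 (still denying).

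**The case against.** The investigators saw this risk, chose sequential consent partly because of it, and claimed only a substantial reduction lasting until the month-3 assessment. Disclosure at that visit is consistent with the claim. A reader might infer that the protocol contradicts itself; it does not.

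A reader might also infer that responder status is biased. The documents do not show that. The Stage 2 consent form and the codebook of measures are not in the supplied text, and the one-sentence summary does not say that the triggering answer, the odds or the payment are disclosed. A participant would have to infer that denying PrEP leads to CM. He would then need documents dated within three months of the second randomization, which someone who started earlier may be unable to produce.

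Nor can it be said that month-3 status went unchecked. The SAP (Acceptability) equates responders with those who filled a prescription and elsewhere refers to verified use, without saying how or when either was established. Still, a request for proof of a fill would not by itself expose someone who denies having one.

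Finally, the analysis is descriptive, the main aims are feasibility and acceptability, and the SAP's past tense suggests that the visits are over.

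All of this stands, and it limits the point to a minor one. It does not remove the gap: the answer the safeguard most needs to protect is given after the safeguard has ended.

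**Conclusion.** The point holds as a minor design improvement. The order of consent and survey is explicit, and the protocol's own defence against gaming stops just short of the answer that sets responder status. No bias is demonstrated, the incentive runs from nothing to a modest sum, and the number of people affected is unknown.

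On the stated assumptions, about one person or fewer would be switched wrongly in most cases (0.35 to 1.4). The MI+CM figure would be flattered by about 1 to 6 points. The MI-only fall depends on how unswitched concealers are recorded at month 6, which the documents do not settle. The assumed concealment rate drives all of these figures, so they show scale and are not estimates. With no tests planned, the consequence here is at most a few misplaced people in a descriptive table. The stronger reason to act is the planned full-scale trial.

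**What to change.** At the same month-3 visit:

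1. Record the dated PrEP evaluation, fill and start items under the Stage 1 consent, extended by a line to cover them.
2. Lock responder status.
3. Only then give the Stage 2 consent, complete the rest of the survey and randomize non-responders.

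The cost is one IRB amendment and a short addition to the Stage 1 consent; visit, staff and items are unchanged. The downside is that ethics review must accept collecting these items before the Stage 2 terms are disclosed, and they are separated from the rest of the survey.

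If the month-3 visits are complete, carry this order into the planned full-scale SMART. For the pilot, list by first-stage arm any second-stage-randomized participant whose verified PrEP fill or start predates his month-3 visit. Documents submitted for Stage 2 CM can supply dates for switched MI-first participants. Note that MI-first documents may otherwise be sparse, since only CM-first participants were paid to submit them in Stage 1; an empty listing in that arm would be weak reassurance. A sentence in the report on how and when PrEP start was ascertained for the second randomization would help the reader.
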